6.1.3.5 Day 180 (6 Months), Visit 5 (+/- 28 days)

- In-person visit
- Follow-up interim medical history and vital signs will be completed.
- Unsolicited AEs, and SAEs, that have occurred since the last contact will be collected.
- Standard antibody testing to assess immune response
- Samples will be collected for immunology/correlative studies (see section [7.3](#)).
- If a participant elects to have a second or third booster vaccination on protocol, the date of administration of this dose will be considered Day 1. The minimum timeframe between booster vaccination doses will be 28 days. Day 180, and Day 360 timepoints, if not yet reached on the original booster vaccination on protocol will be timed according to the participant's last vaccination dose.

6.1.3.6 Day 360, Visit 6 (+/- 28 days)

- In-person visit
- Follow-up interim medical history and vital signs will be completed.
- Unsolicited AEs, and SAEs, that have occurred since the last contact will be collected.
- Samples will be collected for immunology/correlative studies (see section [7.3](#)).
- Standard antibody testing to assess immune response
- Participants will be thanked for participating in the study
- If a participant elects to have a second or third booster vaccination on protocol, the date of administration of this dose will be considered Day 1. The minimum timeframe between booster vaccination doses will be 28 days. Day 360 timepoint, if not yet reached on the original booster vaccination on protocol will be timed according to the participant's last vaccination dose.

6.1.4 Early Termination

- Participants may voluntarily withdraw their consent for participation in the study at any time and for any reason, without penalty. Participants may also withdraw voluntarily from receiving the study intervention for any reason. A site principal investigator may also withdraw a participant from receiving further study intervention.
- Follow-up interim medical history and vital signs will be completed, if possible, whether the participant withdraws from the study or is withdrawn from receiving further study product. Participants will be encouraged to permit continued follow-up of AE/SAEs and to donate scheduled venous blood samples for clinical safety laboratory and immunogenicity evaluations, if possible.
- For participants who withdraw within 7 days of their last dose of vaccine, a 6-month follow-up phone call should be conducted to collect any new SAEs.

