4.5 Study Treatment Compliance

All doses of the investigational study product (IP) will be administered at the study site by medically qualified study personnel and appropriately recorded (date and time) in the participant's medical records. If a participant does not receive vaccine, does not receive a full dose of vaccine, or does not receive all of the planned doses, the reason for the missed or partial dose will be recorded.

Participants in the vaccine-naïve cohorts who miss the second dose of IP due to noncompliance with the visit schedule and not due to a safety pause will still be required to follow the per protocol visit and testing schedule. Unless consent is withdrawn, a participant who withdraws or is withheld from receiving the second dose of study vaccine, if in the vaccine-naïve cohorts, will remain in the study and complete all safety and immunogenicity assessments required through the participant's scheduled end of study. The study site is responsible for ensuring that participants comply with the study windows allowed.

If a participant misses a visit, every effort should be made to contact the participant and complete a visit within the allowed visit window (Study Calendar, Appendix insert). If a participant does not complete a visit within the time window, that visit will be classified as a missed visit and the participant will continue with subsequent scheduled study visits. All safety requirements of the missed visit will be captured and included in the subsequent visit (e.g., clinical laboratory testing, memory aids review for reactogenicity, immunologic testing, as applicable).

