6.3 Criteria for Removal from Study Therapy and Off Study Criteria

Prior to removal from study, effort must be made to have all participants complete a safety visit approximately 28 days after the last vaccine dose of study therapy.

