6.3.2 Off-Study Criteria

- Completed study follow-up period
- Participant requests to be withdrawn from study
- Participant becomes pregnant
- Death
- Screen failure
- PI decision to end the study
- Participant lost to follow-up
- Investigator decision
- Adult permanently loses capacity to consent
- Study is cancelled

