8.1.3 Serious Adverse Events (SAEs)

An adverse event or suspected adverse reaction is considered serious if in the view of the investigator or the sponsor, it results in any of the following:

- Death,
- A life-threatening adverse event (see section [8.1.4](#))
- Inpatient hospitalization or prolongation of existing hospitalization
 - A hospitalization/admission that is pre-planned (i.e., elective or scheduled surgery/chemotherapy arranged prior to the start of the study), a planned hospitalization for pre-existing condition, or a procedure required by the protocol, without a serious deterioration in health, is not considered a serious adverse event.
 - A hospitalization/admission that is solely driven by non-medical reasons (e.g., hospitalization for patient or Participant convenience) is not considered a serious adverse event.
 - Emergency room visits or stays in observation units that do not result in admission to the hospital would not be considered a serious adverse event. The reason for seeking medical care should be evaluated for meeting one of the other serious criteria.
- Persistent or significant incapacity or substantial disruption of the ability to conduct normal life functions
- A congenital anomaly/birth defect
- Important medical events that may not result in death, be life-threatening, or require hospitalization may be considered a serious adverse drug experience when, based upon appropriate medical judgment, they may jeopardize the patient or Participant and may require medical or surgical intervention to prevent one of the outcomes listed in this definition.

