8.7 Reporting Pregnancy

8.7.1 Maternal exposure

Pregnant women are excluded from enrolling due to the possible deleterious effects of the investigational vaccine on the fetus.

If a participant becomes pregnant during the course of the study, the pregnancy will be reported to the Sponsor no later than 24 hours of when the Investigator becomes aware of it. If a pregnancy occurs while on study, to minimize the risks the subject will be withdrawn from the study and follow up care continued by their home obstetrics/gynecological (OB/GYN) doctor.

No inducements, monetary or otherwise, will be offered to terminate a pregnancy. No individuals engaged in the research will have any part in the decisions as to the timing, method, or procedures used to terminate a pregnancy and individuals engaged in the research will have no part in determining the viability of a neonate.

Pregnancy itself is not regarded as an SAE.

The outcome of all pregnancies should be followed up and documented per stand of care. The investigator should notify the Sponsor no later than 24 hours of when the outcome of the pregnancy becomes known.

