8.7.2 Paternal exposure

Male participants should refrain from fathering a child or donating sperm during the study and use effective contraception from first vaccination until 30 days after the last vaccination.

Pregnancy of the participant's partner is not considered to be an AE. However, the outcome of all pregnancies occurring from the date of the first vaccine dose until 1 month after the last dose should, if possible, be followed up and documented. Pregnant partners may be offered the opportunity to participate in an institutional pregnancy registry protocol (e.g., the NIH IRP pregnancy registry study) to provide data about the outcome of the pregnancy for safety reporting purposes.

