11 STATISTICAL CONSIDERATIONS

11.1 Study Hypotheses

There is no hypothesis testing in this study; the study is intended to develop modestly precise estimates of parameters which reflect potential efficacy.

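### The 6-month SAE call reaches only participants who withdraw within 7 days of a dose, and the sections on late SAEs and on pregnancy before dose 2 do not agree with one another

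*Combined protocol and SAP*

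**What the plan says.** **After early termination.** Section 6.1.4 reads: "For participants who withdraw within 7 days of their last dose of vaccine, a 6-month follow-up phone call should be conducted". The call is for any new SAE, with no relatedness condition. For an exit at any time, the same section asks for an interim history and vital signs if possible, and for encouragement to allow continued AE/SAE follow-up and scheduled blood samples. It applies these terms alike to leaving the study and to being withdrawn from further product.

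**Removal.** Section 6.3 asks for an effort to have every participant "complete a safety visit approximately 28 days after the last vaccine dose". Section 6.3.1 adds that, with consent, AEs are followed to resolution.

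**Missed dose 2.** Under 4.5, a vaccine-naïve participant who withdraws or is withheld from dose 2, without withdrawing consent, "will remain in the study and complete all safety and immunogenicity assessments required". No equivalent sentence covers the booster cohorts.

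**Late SAEs.** The primary endpoint in 3.2 is SAEs over the whole study, whatever their cause. Section 8.3, repeated in the keys to both study calendars (Appendix F note f, Appendix G note h), limits recording after 28 days to related SAEs.

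**Pregnancy.** It is a reason to stop treatment (6.3.1) and also an off-study criterion: "Participant becomes pregnant" (6.3.2). Section 8.7.1 says that "to minimize the risks the subject will be withdrawn from the study". It also expects every pregnancy outcome to be followed up and documented, and the sponsor told within 24 hours of the outcome becoming known.

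**The concern.** Seven days is the solicited-reaction window. The call serves the SAE endpoint, which has no such limit. Participants who stay are asked about SAEs in person at the 6-month visit (6.1.2.5, 6.1.3.5). Everyone who leaves before that visit misses the question, but only the earliest leavers get a call in its place.

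This bears on a primary result. Section 11.1 states "There is no hypothesis testing in this study", so the reported percentages and their intervals are the findings. The Safety Set is everyone with at least one injection (11.4.1.4), SAEs are reported as number and percentage (11.4.2.2), and dosed leavers are not replaced (6.3.3). A leaver whose later SAE is never learned of stays in the denominator as a participant without an event. By this route the SAE percentage can only be understated.

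Two neighbouring conflicts affect the same data. If sites follow 8.3, the call and the endpoint collect different events. If a participant becomes pregnant before dose 2, 4.5 and 6.3.2 give opposite answers on whether her assessments continue.

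**Working it through.** No sample size, power or error rate is involved, and the plan states no figure to reproduce. The check is day counts plus a comparison of sections.

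**1. Share of follow-up covered by the trigger (3.1, 6.1.4).**
- Vaccine-naïve: dose 2 on Day 29, follow-up to Day 394. 394 − 29 = 365 days; 7/365 = 1.9%.
- Booster: dose on Day 1, follow-up to Day 360. 360 − 1 = 359 days; 7/359 = 1.9%.
- Unsolicited-AE window of 28 days (3.2): 28 − 7 = 21 days lie outside the trigger; 21/28 = 75%.
- Time from the last scheduled dose to the 6-month visit: 209 − 29 = 180 days (naïve) and 180 − 1 = 179 days (booster). Beyond the first 7 days this leaves 180 − 7 = 173 and 179 − 7 = 172 days in which an exit misses the visit without triggering the call.

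These are shares of calendar time, not of participants. The documents give neither a dropout rate nor the timing of dropout, so they cannot be turned into a headcount.

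**2. What a leaver has, by day of exit after the last dose.**

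| Provision | Exit by day 7 | Exit after day 7, before the 6-month visit |
|---|---|---|
| History and vital signs at exit, if possible (6.1.4) | yes | yes |
| Encouragement to permit AE/SAE follow-up and samples (6.1.4) | yes | yes |
| Safety visit sought near day 28 (6.3) | yes | yes, if still ahead |
| AEs followed to resolution, with consent (6.3.1, on stopping treatment) | yes | yes |
| Call at 6 months for new SAEs (6.1.4) | yes | **no** |

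The difference is the last row. Following a known AE to resolution does not by itself find a new SAE. The visit near day 28 also falls before the 6-week (42-day) myocarditis/pericarditis halting window closes (8.9.1).

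**3. Stopping product versus leaving the study.** Section 4.5 separates the two for the naïve cohorts, and Appendix E does so for myocarditis and pericarditis: vaccination stops and follow-up continues. Section 6.1.4 does not separate them. A booster participant withdrawn from an optional further dose is covered only by 6.1.4 and by the follow-up that 6.3.1 leaves to the investigator to specify.

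**4. Which SAEs count after day 28.** Section 3.2: all. Section 6.1.4: any new SAE. The 6-month and final visits (6.1.2.5, 6.1.2.6, 6.1.3.5, 6.1.3.6): SAEs since the last contact, with no relatedness condition. Section 8.3 and the two calendar notes: related SAEs only. These cannot all govern.

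**5. Pregnancy before dose 2.** A negative test is required before each vaccination (7.3.1, Appendix F note c), so she is withheld from dose 2. Section 4.5 then keeps her on all assessments unless she withdraws consent; 6.3.2 and 8.7.1 take her off study. That is a direct conflict, confined to vaccine-naïve participants between the two doses. More generally, "A congenital anomaly/birth defect" is an SAE criterion (8.1.3) and 8.7.1 wants the outcome, but no route is named for obtaining it from a participant once she has left the study.

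**The case against.** The strongest reply is that later leavers do have provision. Encouragement to permit follow-up applies at any exit, 6.3 seeks a day-28 visit for all, and 6.3.1 follows AEs to resolution with consent. Once consent is withdrawn, voluntary contact is all any protocol can ask, and a wider call would be voluntary too. This stands against a reading that some may infer, that nobody who leaves after day 7 has any safety follow-up. It does not explain why a scheduled question about new SAEs is put only to the earliest leavers.

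Second, under 8.3 most late unrelated SAEs need not be recorded even for those who stay, so the call might add little. That is true if 8.3 governs, which is why that conflict must be settled with the call.

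Third, 4.5 is the specific rule for a missed dose 2 and can be read together with the exit assessment in 6.1.4. For naïve participants this largely stands. The booster cohorts have no such rule, though the gap there is small because further doses are optional.

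Fourth, a reader might infer that a pregnant participant is lost to all follow-up. The documents do not support this: 8.7.1 requires the outcome to be followed and reported, and the day-28 visit applies to her too. What is missing is the mechanism.

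Fifth, the 6-month visit is also a cut-off, and those who leave after it get no call although follow-up runs to Day 394 or 360. This is fair. The case for it is that the call then replaces the visit that the leaver missed.

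**Conclusion.** The point holds as a gap in ascertainment of a primary safety endpoint, with two conflicts between sections beside it. The call's trigger spans 1.9% of post-dose follow-up and leaves 21 of the 28 unsolicited-AE days outside it. It rests on reading the 6-month call as a substitute for the 6-month visit.

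How many participants this affects is unknown. Any headcount would need an assumed dropout rate and timing, and exits prompted by a reaction could cluster near the dose, inside the trigger. The direction is clear, since uncollected SAEs lower the reported percentage; the size is not.

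The clash between 4.5 and 6.3.2/8.7.1 is direct but narrow. The documents do not show which withdrawal rule should prevail, and a reader should not infer from this point that pregnancy ought to come off the off-study list. The point justifies an amendment. It does not undermine the design.

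**What to change.** 1. In 6.1.4, replace the 7-day condition with withdrawal at any time before the participant's 6-month visit, subject to the participant's agreement.
2. In 6.1.4, state that participants who stop study product without withdrawing consent continue scheduled safety collection in all cohorts, as 4.5 already provides for the vaccine-naïve cohorts.
3. Reconcile 8.3, Appendix F note f and Appendix G note h with 3.2 and 6.1.4, so that the call and the endpoint collect the same SAEs.
4. Reconcile 4.5 with 6.3.2 and 8.7.1 for a participant who becomes pregnant before dose 2, and state how the pregnancy outcome required by 8.7.1 will be obtained with her consent. The choice of withdrawal rule is the sponsor's.

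The cost is amendment wording and one telephone call per agreeing leaver. Some will decline. No dose, eligibility criterion or vaccination-stopping rule needs to change for items 1 to 3.

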6.1.5 Unscheduled Study Visits

At any time during the study a participant can also be seen for an unscheduled visit. An unscheduled visit may be prompted by reactogenicity issues, unsolicited new or ongoing adverse events.

When interim contacts or visits are completed in response to participant reports of AEs, study staff will assess the reported event clinically and provide or refer the participant to appropriate medical care. All AEs will be evaluated and reported as required. All interim contacts and visits will be documented in participants' study records and on applicable data collection forms.

The site Staff may also decide to make reminder telephone calls to inform the participant about visits, review study requirements, or follow-up on ongoing or outstanding issues.

6.2 Withdrawal from the Study or Discontinuation of the Study Product

Participants may voluntarily withdraw their consent for study participation at any time without penalty or loss of benefits to which they are otherwise entitled.

6.3 Criteria for Removal from Study Therapy and Off Study Criteria

Prior to removal from study, effort must be made to have all participants complete a safety visit approximately 28 days after the last vaccine dose of study therapy.

6.3.1 Criteria for removal from study treatment

- Participant requests to be withdrawn
- Unacceptable toxicity
- Allergic reactions, hyperimmune responses and/or SAEs considered related to the vaccine
- Participant becomes pregnant
- Investigator decision

The investigator should be explicit regarding study follow-up (e.g., safety follow-up) that might be carried out despite the fact the Participant will not receive further study product. If the Participant consents, every attempt will be made to follow all AEs through resolution. The procedures that collect safety data for the purposes of research must be inclusive in the original informed consent or the investigator may seek subsequent informed consent using an IRB-approved consent form with the revised procedures.

The investigator will inform the Participant that already collected data will be retained and analyzed even if the Participant withdraws from this study.

6.3.2 Off-Study Criteria

- Completed study follow-up period
- Participant requests to be withdrawn from study
- Participant becomes pregnant
- Death
- Screen failure
- PI decision to end the study
- Participant lost to follow-up
- Investigator decision
- Adult permanently loses capacity to consent
- Study is cancelled

6.3.3 Participant Replacement

Participants who withdraw, or are withdrawn from this study, or are lost to follow-up after signing the informed consent form (ICF) and administration of the study product will not be replaced. Participants who withdraw, or are withdrawn from this study, or are lost to follow-up after signing the ICF but before administration of the study product may be replaced.

6.3.4 Lost to Follow-up

A participant will be considered lost to follow-up if he or she fails to return for 3 consecutive scheduled visits and is unable to be contacted by the study site staff.

The following actions must be taken if a participant fails to return to the clinic for a required study visit:

- The site will attempt to contact the participant and reschedule the missed visit within 3 days and counsel the participant on the importance of maintaining the assigned visit schedule and ascertain if the participant wishes to and/or should continue in the study.
- Before a participant is deemed lost to follow-up, the investigator or designee will make every effort to regain contact with the participant (where possible, 3 telephone calls and, if necessary, an IRB approved certified letter to the participant's last known mailing address or local equivalent methods). These contact attempts should be documented in the participant's medical record or study file.
- Should the participant continue to be unreachable, he or she will be considered to have withdrawn from the study with a primary reason of lost to follow-up.

6.3.5 Study Termination, Discontinuation and Closure

This study may be temporarily suspended or prematurely terminated if there is sufficient reasonable cause. Written notification, documenting the reason for study suspension or termination, will be provided by the suspending or terminating party to study participants, investigator, funding agency, the Investigational New Drug (IND) sponsor and regulatory authorities. If the study is prematurely terminated or suspended, the Principal Investigator (PI) will promptly inform study participants, the Institutional Review Board (IRB), and sponsor and will provide the reason(s) for the termination or suspension. Study participants will be contacted, as applicable, and be informed of changes to study visit schedule.

Circumstances that may warrant termination or suspension include, but are not limited to:

- Determination of unexpected, significant, or unacceptable risk to participants
- Insufficient compliance to protocol requirements
- Data that are not sufficiently complete and/or evaluable
- Determination that the primary endpoint has been met
- Determination of futility

Study may resume once concerns about safety, protocol compliance, and data quality are addressed, and satisfy the sponsor, IRB and as applicable, the Food and Drug Administration (FDA).

7 DESCRIPTION OF CLINICAL AND LABORATORY EVALUATIONS

For timepoints see the Study Calendar in Appendix ([Appendix E](#)).

7.1 Clinical Evaluations

7.1.1 Medical History

Will be obtained by interview of the potential participant and review of their medical records. Participants will be queried regarding history of cancer and any significant medical disorders of the head, eyes, ears, nose, throat (HEENT), mouth, cardiovascular system, lungs, gastrointestinal tract, liver, pancreas, kidney, urologic, nervous system, blood, lymph glands, endocrine system, musculoskeletal system, skin, and genital/reproductive tract. A history of any allergies, immunodeficiency, psychiatric illness, and autoimmune disease will be solicited.

